2.7. Building Capacity

The pilot phase of this proposed study has led to new research activity collaboratively through the James Cook University. This included new research nurses and medical team. The collaboration using the academic background of the Brisbane and Gold Coast based research team with extensive track record in the field of ARF research has been established and resulted in the funding of the pilot phase by the Children's Health Foundation and by the Medical Research Future Fund (MRFF) for the current study. Further collaboration and capacity building has been achieved with a network of researchers including local indigenous stake holders, remote health services, retrieval services and metropolitan/tertiary hospitals in Cairns and Townsville. It is anticipated with the expansion to additional sites that this network will expand and increased contribution by local communities and indigenous researchers will be achieved.

Aboriginal and Torres Strait Islander people represent a large workforce within TCHHS and this workforce has been relied upon throughout the entire process of implementing research on-the-ground. Without this assistance the pilot phase would not have been able to conduct the research to its entirety. The pilot phase provided education to and received support from all clinical health streams such as physiotherapy, occupational therapy, dietitians, speech pathology, pharmacy, nursing and medicine; however, support has also included administration, stores and hospital courier services in assistance with the research.

From being present and developing research capacity within the predominant Aboriginal Torres Strait Island population community, further contacts and discussion around potential future research projects that would benefit this community have now occurred and this effect will snowball into developing further capacity and beneficial impact for the health of Aboriginal and Torres Strait Islander people. Further collaborations with other research groups have been a result in the betterment of the planning, conduct and dissemination of research throughout these connections. Being present within the community makes a

significant difference and very much matters to the community in improving trust, reliability and further collaborations/consultations together (addressing NHMRC indigenous core value, **Respect**).

2.8. Summary

In summary this project is governed by the following overarching principles:

- 1.) This project is ***driven by consumer request*** and will reduce pressure on North Queensland rural and remote emergency departments by ***reducing emergency transfers*** of children with ARF allowing for admission to a local ward rather than prolonged stay in the ED awaiting transfer to higher level of care.
- 2.) This project will ***reduce length of stay in ED (bed block)*** and free up hospital beds.
- 3.) This project will ***reduce the gap in respiratory care*** for ***Indigenous children*** with ARF in rural and remote health care settings from the time of presentation to discharge using existing resources of existing guidelines adopted in regional and metropolitan hospitals in Queensland (equality of care). This will build knowledge, skillset and confidence of local remote clinicians in caring for a young child in the emergency setting with the appropriate management which can reduce the risk of escalation and transfer.
- 4.) This project will ***reduce health care costs*** driven by a reduced need for aeromedical transport; greater patient satisfaction and reduced socio-economic burden on families (acute care can be provided safely in their remote hospital).

3. STUDY AIMS

3.1. The aim of this study is to evaluate that the implementation of an acute respiratory care bundle using current existing Queensland Health standards of care in children presenting to rural and remote hospitals with acute respiratory failure leads to service delivery improvements and reduced hospital transfers of these children.

3.2. Objectives

1. To evaluate the implementation of a respiratory care bundle, using existing current best Queensland Health practice guidelines that are adapted to each individual context in existing acute paediatric care services in remote and rural hospitals to reduce the proportion of children transferred to a tertiary hospital and reduce health care costs.
2. To demonstrate that the implementation of the respiratory care bundle reduces the length of stay in acute care settings and health care costs.
3. To assess and measure the acceptance and compliance of the clinical staff of the respiratory care package.
4. To demonstrate sustainability of the respiratory care bundle beyond the study.

3.3. Hypotheses

The primary hypothesis of this study is that the implementation of an acute respiratory care bundle reduces the proportion of children transferred to higher level of care compared to existing care pathways.

3.4. Primary Outcome

The **primary outcome** is the proportion of yearly hospital transfers of infants and children aged 0-4 years with ARF including bronchiolitis cared for with the new respiratory care bundle in comparison to numbers under the existing respiratory pathways.

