2. INTRODUCTION AND BACKGROUND

2.1. Background and Rationale

Acute respiratory distress in children is the most common reason for emergency department (ED) presentations in Australia and is the most common reason for hospital admission in children less than 1 year of age (56% of all admissions to hospital) and the most common reason for paediatric aeromedical transfer in remote Australia [1, 2]. If high level of respiratory support is required, children require admission to a paediatric intensive care unit (PICU) in a tertiary hospital, necessitating a costly transfer by a retrieval service and impacting on families as they must care for their child outside their regular environment. Many rural and remote Australian hospitals experience delays in retrieval due to the distances involved, available assets to undertake the transport and impacts of weather conditions on safe transport. These transfers have an intrinsic risk associated with them. The delay in retrieval often results in an extended stay in the emergency department for these children, placing increased burden on ED staff and resources. To reduce this burden, staff in rural and remote hospitals may be able to safely deliver acute respiratory support to these children in the inpatient setting, building on evidence and research that has been undertaken in metropolitan centres by our research group.

On a global scale, the respiratory disease remains the leading cause of death in children. In under resourced countries, children presenting to hospitals with severe pneumonia have a mortality rate between 13-20% and most deaths occurring with hypoxaemia before therapeutic benefit of antimicrobials [3]. In developed countries in contrast, the mortality due to severe respiratory disease is relatively low, accounting for 1.1 % of deaths in PICU [1, 4]. In Australia, 28% of non-elective intensive care admissions for children are due to acute respiratory failure (ARF), with bronchiolitis representing 15%, pneumonia 7% and asthma 6% [1]. The direct cost due to Australia/New Zealand hospitalisation increased fourfold from A\$ 11.4 M in 2002 to A\$ 44.3 million in 2014 (indexed for inflation), due to severe bronchiolitis alone [5-7].

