3.8. Eligibility, Inclusion and Exclusion Criteria

3.8.1 Inclusion Criteria for Data Capture

- **Infants with bronchiolitis admitted to hospital, aged < 12 months** with or without oxygen requirement, defined as acute onset of respiratory disease, presenting with increased respiratory rate, cough, increased work of breathing, rhinorrhoea, increased body temperature, widespread crackles or wheeze and reduced fluid intake. Observational data will be obtained for these infants.
- **Children admitted to hospital aged 0-4 years with acute respiratory symptoms**, presenting with increased respiratory rate, with or without oxygen requirement, with or

without increased work of breathing and wheeze, increased body temperature and reduced fluid intake. Note, there are only few infants <12 months of age that are presenting to hospital with respiratory symptoms other than bronchiolitis. Observational data will be obtained for these children.

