3.8.3 Exclusion Criteria

There are no formal patient exclusion criteria as the intent of the study is to observe and monitor all episodes when a child presents with acute respiratory failure (including bronchiolitis) to one of the participating hospitals.

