8.2 Data Analysis

Generalised linear mixed models (GLMMs) will be used to account for cluster hospital effects with adjustment for the rollout time of the intervention and potential district effect and estimate the change in the proportions of PICU transfers (using a logistic link function) as well as the length of stay in acute care settings (using Poisson or negative binomial distributions) under the intervention condition, compared with those under the control condition. Model fit and assumption testing will

be conducted as appropriate within the GLMM framework and significance will be set at $p < 0.05$. The GLMM can handle missing data in the outcome variable under the ignorable mechanism (such as missing completely at random).

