9. ADVERSE EVENTS AND RISKS

9.1 Adverse Event Definitions

Adverse Event (AE)

Adverse event data is collected as part of the study design and will form part of the secondary outcomes of the study. Conditions that are present at screening and do not deteriorate will not be considered adverse events. These outcomes will be routinely reported via standard hospital internal reporting methods/risk management processes. If any of the attending clinicians suspect an adverse event that is related to the study design, such an adverse event will be immediately reported to the Chief Investigator and Townsville HHS HREC.

For the purposes of this study the site investigator is responsible for recording all AEs, regardless of their relationship to study intervention. Conditions that are present at screening and do not deteriorate will not be considered AEs.

Serious adverse event (SAE)

SAEs for this study are defined as:

- Hypoxaemia leading to cardiac massage which the clinician believes is related to one of the study interventions
- Cardiac arrest: Loss of spontaneous cardiac output
- Mortality (all events will be reported)
- OR any life-threatening medical event or reaction which the clinician believes may be study related

Adverse event (AE)

AEs are defined as but limited to the following:

- Severe hypoxaemia with saturations <80% for longer than 1 minute
- Pneumothorax
- Unexpected need for endotracheal tube placement
- Bradycardia: bradycardia not requiring treatment; bradycardia of <60/min [27, 28]

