9.5 Risk/benefit analysis

Individual patient care will be driven by standard practice before and after implementation of the respiratory bundle. An independent data safety monitoring board (DSMB) will be tasked to monitor study progression and assess trajectory of study outcome.

Potential risks.

This study is performed in a health care setting with a relatively high staff turnover. This may lead to decreased adherence to the respiratory care bundle. Mitigation: the education will be part of the required mandatory education in each hospital.

A delay in the transfer of patients who definitively require high level of care. Mitigation: the bundle sets robust boundaries and thresholds of when escalation must occur and hence this is unlikely to occur. Patient care will occur within the standard clinical treatment framework.

Potential benefits.

Reduction of unnecessary transfers to higher level of care. Increased clinical staff knowledge, confidence and skillset caring for children less than 5 years with acute respiratory failure. Increased clinical staff and consumer satisfaction.

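### A child who dies on site before transfer scores as not transferred, so the transfer result needs a death-inclusive sensitivity analysis and mortality by phase beside it

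*Protocol*

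**What the plan says.** Protocol 3.4 defines the primary outcome as "the proportion of yearly hospital transfers of infants and children aged 0-4 years with ARF including bronchiolitis", compared between the bundle and existing care. Section 3.3 fixes the direction of success: "the implementation of an acute respiratory care bundle reduces the proportion of children transferred to higher level of care compared to existing care pathways". Section 8.2 analyses it as a binary outcome in a mixed model, to "estimate the change in the proportions of PICU transfers (using a logistic link function". The destination is worded differently across these sections, but an on-site death is a transfer under none of the wordings.

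The population in 3.8.1 is "Children admitted to hospital aged 0-4 years with acute respiratory symptoms", together with admitted infants with bronchiolitis, and 3.8.3 adds: "There are no formal patient exclusion criteria".

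On risk, 9.5 lists "A delay in the transfer of patients who definitively require high level of care". Section 6.2.3 puts to the expert working group whether the availability of high-flow could delay or cancel a retrieval and so delay the best care. Section 2.1 notes that "Many rural and remote Australian hospitals experience delays in retrieval due to the distances involved, available assets to undertake the transport".

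Deaths are captured. Section 9.1 lists among the serious adverse events "Mortality (all events will be reported", and counts adverse-event data among the secondary outcomes. Section 9.2 sends these events to the ethics committee, and 9.5 provides for an independent data safety monitoring board. The outcome lists in 3.5 to 3.7 do not name mortality; the nearest entry is item 7 of 3.6, on reduced adverse effects.

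**The concern.** Transfer and on-site death compete: a child who dies before retrieval can no longer be transferred. When the event is transfer alone, fewer events are better and no one is excluded, that child stays in the denominator without an event. The primary outcome then cannot separate a child who recovered locally from one who died waiting.

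This matters more here than in most service trials, because the bundle is meant to keep more sick children at the local hospital and the protocol itself names late transfer as a risk of doing so. If untransferred deaths rose under the bundle, part of an apparent fall in transfers would be those deaths. Even if they did not rise, a reader of the main result would want to see that.

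**Working it through.** **The plan's own figure.** Section 8.1 states over 85% power for 25% versus 12.5%, with 14 hospitals, 4 steps, 18 children per hospital per time point (90 per hospital, 1,260 in total), an intracluster correlation of 0.1 and a two-sided 5% test. The Hussey and Hughes variance for 14 clusters (I), 5 periods (T) and a 3/4/4/3 split is

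Var = I·s²(s² + T·τ²) / [(I·U − W)s² + (U² + I·T·U − T·W − I·V)τ²].

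- U = 35 treated hospital-periods.
- W = 0² + 3² + 7² + 11² + 14² = 375.
- V = 3·16 + 4·9 + 4·4 + 3·1 = 103.
- Variance averaged over arms = (0.1875 + 0.1094)/2 = 0.1484, so τ² = 0.1 × 0.1484 = 0.01484 and s² = 0.9 × 0.1484/18 = 0.00742.

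The standard error is 0.0371 and the power is Φ(0.125/0.0371 − 1.96) = 92.1%. With the control-rate variance it is 85.1%. Only the most conservative variant (control-rate variance and the correlation applied to the within-cluster variance) falls lower, to 81–82%. The stated figure is reproduced under ordinary choices, and this point does not dispute it.

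**Children per phase.** Control hospital-periods are 3·1 + 4·2 + 4·3 + 3·4 = 35 of 70. At 18 children each, that is 630 control and 630 intervention. The even split rests on the equal cell sizes assumed in 8.1.

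**What the scoring does.** Let T be the proportion transferred and d the proportion who die untransferred, in control (c) and intervention (i).

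- Transfer alone: difference = Tc − Ti.
- Transfer or death before transfer: difference = (Tc + dc) − (Ti + di) = (Tc − Ti) − (di − dc).

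On the risk-difference scale the two differ by di − dc. If untransferred deaths are equally frequent in both phases, the difference does not change. If they are more frequent under the bundle, transfer alone flatters it; if less frequent, transfer alone understates it.

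**Size.** The documents give no rate of death before transfer, so the range is an assumption: one to five more such deaths in the intervention phase than in control.

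- One: 1/630 = 0.16 points; 0.16/12.5 = 1.3% of the target reduction.
- Five: 5/630 = 0.79 points; 0.79/12.5 = 6.3% of the target reduction.

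**Power of the death-inclusive analysis.** Using the 92.1% variant, with all excess deaths in the intervention phase and transfers at 12.5%:

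| Excess deaths, % of 630 | Number | Event proportion under bundle | Power |
|---|---|---|---|
| 0 | 0 | 12.5% | 92.1% |
| 0.1 | 0.6 | 12.6% | 91.6% |
| 0.5 | 3.2 | 13.0% | 89.5% |
| 1.0 | 6.3 | 13.5% | 86.5% |

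The power for transfer alone, which stays primary, does not change.

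**The case against.** The strongest case against the point runs as follows.

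- **This belongs in the analysis plan.** The protocol does not state the scoring rule in words, and rules for intervening events are often left to a later document that is not shown here. This stands in part: a sensitivity analysis may already be planned there. But the event itself is fixed in 3.4 and 8.2, and the outcome lists that omit mortality are in the protocol.
- **The scoring is symmetric.** A reader might infer that the definition always favours the bundle. The documents do not support that. The same rule applies in control periods, where an untransferred death lowers the control proportion and works against the bundle. The retrieval delays described in 2.1 belong to existing care, so they bear on control-phase deaths just as much. This stands in full.
- **Safety is covered elsewhere.** A reader might also infer that deaths go unseen. They do not: all are reported, 9.2 sets a 24 to 72 hour route to the ethics committee, a monitoring board is planned, and 9.5 judges harmful delay unlikely because of the bundle's escalation limits. This stands, but it does not change how the primary outcome scores a death.
- **The denominator is not certain.** Section 3.8.1 speaks of admitted children, 3.8.3 of children who present. A child who dies in the emergency department before admission may be outside the count altogether. The point is therefore limited to admitted children.
- **The aim is a service outcome.** Sections 3.1 and 3.3 concern transfers, and the protocol nowhere defines success as survival without transfer. A composite would be almost all transfers and would weigh a death as one transfer. This is a sound reason not to insist on changing the primary event.

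**Conclusion.** The point holds in limited form and is minor. As defined, an admitted child who dies on site before transfer takes the favourable value in either phase. The comparison is biased towards the bundle only if such deaths are more frequent under it. The protocol raises that scenario as a risk (9.5) and as a question (6.2.3), but gives no evidence that it will happen.

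The likely numerical effect is small: 0.16 to 0.79 points, or about 1% to 6% of the 12.5-point target. That rests on two assumptions, an even split of 630 children per phase and one to five excess deaths under the bundle. No local death rate is given, and 2.1 describes mortality in developed countries as relatively low. What is at stake is whether a fall in transfers can be read correctly, together with the safety picture beside it, and not the power of the trial.

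**What to change.** In 8.2, prespecify a key sensitivity analysis of the primary outcome in which the event is transfer to a higher level of care or death at the participating hospital before transfer, using the same mixed model. In 3.5, name mortality as a secondary outcome, in total and before transfer, by control and intervention phase, and report it beside the transfer result. Making the composite the primary event is open to the sponsor but not required.

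The cost is one extra analysis, which transfers will dominate, and a protocol amendment that section 12 sends to the ethics committee for approval. No new data are needed, since 9.1 already requires every death to be reported. Section 5.1 keeps the investigators blinded to outcome data until database lock, so the rule can still be set without knowledge of the results.

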3.5. Secondary Clinical Outcomes

The **secondary clinical outcomes** are:

1. length of stay in hospital
2. length of oxygen therapy
3. health care costs including transport costs and social opportunity costs (including back transfer)
4. sustainability and adherence to the respiratory care bundle beyond the intervention period measured with the Normalisation Process Theory
5. measurement of the proportion of infants and children transferred to a tertiary hospital post implementation
6. consumer satisfaction survey – includes staff and parents/carers

3.6. Secondary Health Service Research Outcomes

The *health service research outcomes* are:

1. Reduced health care resource utilisation in the form of reduced hospital transfers for higher level of care.
2. Satisfaction with education and competencies associated with ARF management
3. Electronic medical record prompts are operational
4. Use of evidence-based-practice (EBP) is cost-effective
5. Patient/Carer satisfaction
6. Availability of the associated materials, which are cost-effective
7. Reduced adverse effects for children with ARF or other outcomes.

3.7. Secondary Implementation Outcomes

The *evaluation of the implementation outcomes* will be measured using the Society for Implementation Research Instrument Toolkit (SIRC). Outcomes assessed will include acceptability, feasibility, adoption, penetration, adaptability and sustainability measures. Furthermore, the engaging, executing, planning, reflecting and evaluation measures will be captured. We will investigate the following specific Implementation Outcomes:

1. Use of the new respiratory care bundle as a routine treatment
2. Feasibility of the implemented changes
3. Acceptability of the EBP
4. Satisfaction with the use of EBP (all stakeholders)
5. Satisfaction with the implementation process
6. Evaluation of the EBP implementation is shown as acceptable and commendable/highly valued
7. Recommended for further implementation in other healthcare settings

3.8. Eligibility, Inclusion and Exclusion Criteria

3.8.1 Inclusion Criteria for Data Capture

- **Infants with bronchiolitis admitted to hospital, aged < 12 months** with or without oxygen requirement, defined as acute onset of respiratory disease, presenting with increased respiratory rate, cough, increased work of breathing, rhinorrhoea, increased body temperature, widespread crackles or wheeze and reduced fluid intake. Observational data will be obtained for these infants.
- **Children admitted to hospital aged 0-4 years with acute respiratory symptoms**, presenting with increased respiratory rate, with or without oxygen requirement, with or

without increased work of breathing and wheeze, increased body temperature and reduced fluid intake. Note, there are only few infants <12 months of age that are presenting to hospital with respiratory symptoms other than bronchiolitis. Observational data will be obtained for these children.

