5. RECRUITMENT, RANDOMISATION AND CONSENT

5.1. Recruitment and randomisation

This project is a science implementation evaluation study implementing an existing clinical respiratory care bundle for children with ARF using a stepped wedge cluster randomised trial design. Each participating hospital is the unit of randomisation, and target for primary analysis. There is no individual participant randomisation required. Clinical indication will dictate medical care. The implementation start date will be randomly allocated to each hospital using a computer-generated sequence and using a stratification per hospital and health services (HHS). Therefore, no individual patient recruitment will occur, however outcome data of individual data of children presenting with and admitted/transferred with ARF obtained during and after the implementation will be used in comparison to historical data of children with ARF previously presented/admitted and/or retrieved at the participating hospitals. We therefore only seek a Public Health Act (PHA) approval to include all participating hospitals and enable the research team to collect and review patient information during the hospital admission period or where relevant data on transfer to higher level of care occurs. All individual patient data will be de-identified for the purpose of study analysis.

The study investigators will remain blinded to outcome data until the study database is locked for analysis.

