7. DATA

7.1 Data Collection

The precise data to be collected and their sources for the study are given as per the below Clinical Research Forms (CRF) and datasets:

CRF 1	Clinical data
Source for Clinical data: Patient’s medical records, including observations and medical/nursing notes, discharge summary and admission form. Includes EDIS export to locate the relevant patients to obtain data from.	
CRF 2	Health Economy data (specifically aimed at out-of-pocket costs for families and measures of quality of life)
Source for Health Economy data: Use of the GenPrem instrument will be for the parent as proxy for the child and as the parent for their own experience with their child’s admission to hospital.	
CRF 3	Implementation Science data (specifically aimed at knowledge, skill retention and fidelity)
Source for Implementation Science data: The Normalisation Process Theory tool will be used and adapted for the staff survey. This survey will be in paper and electronic format depending on what is most suitable for the local team.	

Other Datasets & Collection includes:

Health Economy data (specifically aimed at health care and transportation costs) – sourced as per current Qld Health per day admission costings for the ward and/or Intensive Care and transfer/retrieval costs.

Health Economy data (specifically aimed at implementation costs which includes education costs) – sourced by capturing all education records and monitoring/capturing data on the movement of the transient staff in these regions.

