Data will be collected in an online REDCap database. In each site the emergency admissions will be screened for children 0-4 years of age presenting with respiratory symptoms. Data on the baseline demographics, physiology at presentation and initial medical management will be captured. Length of hospital stay, length of oxygen therapy, type of oxygen therapy, and amount of oxygen resources will be captured. Further information will be captured on methods of oxygen therapy. Adverse events will be recorded. For children who required transfer to high level of care, vital signs and clinical diagnosis and medical therapy provided at time of decision to transfer will be collected. Data on respiratory support during transfer, mode and length of transport and data on treatment in accepting hospital and length of hospital stay will be collected. Adherence to the respiratory care bundle will be measured by the number of frequency of deviations from the protocol.

Twelve parents per hospital using a face-to-face structured interview will complete a paediatric proxy health related quality of life measurer (PedsQL).

Historical Control. Admissions (HBCIS) to the participating hospitals in year 2016-2022 will be screened using the same screening log as in the main protocol (Year 2020-2022 will be separately analysed due to impact of COVID-19 pandemic) and the same data collection as above used.

Time Points for Data Collection. All physiological (heart and respiratory rate, temperature) and blood parameters (arterial gases) that are captured in the medical records during the hospital admission and where relevant during the transfer for higher level of care. If admitted to a tertiary hospital, data on respiratory support provided will be captured.

Specific data

The specific data set mirrors in its basic form the data captured in our previous 3 large RCT's using nasal high-flow in children with ARF or bronchiolitis. Additional data on out-of-pocket expenses and lost income will be recorded.

Background data:

Background data collection will be collected as per the CRF. Below outlines some of the specifics which continue the same data collection of the 3 large RCT's.

Demographics:

- Age (on admission)
- Gender
- Weight (on admission)
- Ethnicity
- Diagnosis at admission
- History and risk factors
 - Prematurity (<37 weeks at birth)
 - Previous neonatal respiratory support post delivery
 - Previous Intensive Care admission post delivery

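### Eligibility is defined by admission, by presentation, and by admission or transfer in different sections, and the primary outcome names no denominator, so the transfer proportion could move with admission practice alone

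*Protocol*

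**What the plan says.** The protocol describes the population in several ways.

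- **Admitted.** Section 3.8.1 covers "Infants with bronchiolitis admitted to hospital, aged < 12 months" and "Children admitted to hospital aged 0-4 years with acute respiratory symptoms". The synopsis repeats this. The planning rate in section 8.1 is also built on admissions: 2,532 children admitted in 2016-2019, of whom 25% were transferred.
- **Presenting.** Section 3.8.3 gives as the reason for having no exclusions that the study will "observe and monitor all episodes when a child presents with acute respiratory failure (including bronchiolitis) to one of the participating hospitals".
- **Admitted or transferred.** Section 5.1 uses "outcome data of individual data of children presenting with and admitted/transferred with ARF".
- **Mixed.** Section 7.1 states: "In each site the emergency admissions will be screened for children 0-4 years of age presenting with respiratory symptoms". For the clinical data source it adds: "Includes EDIS export to locate the relevant patients to obtain data from". Historical cases come from HBCIS admissions instead.

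Section 3.4 defines the primary outcome as a proportion of transfers among children aged 0-4 years with ARF, without naming admissions or presentations as the base. Section 2.8 describes the bundle as "allowing for admission to a local ward rather than prolonged stay in the ED awaiting transfer to higher level of care".

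**The concern.** A proportion is only as stable as its denominator. Under section 3.8.1 a child enters the data by being admitted. The clinical criteria are broad: oxygen requirement and increased work of breathing may each be present or absent in the 0-4 year group. Admission is therefore the main gate. After crossover that decision is made by staff trained in the bundle, who know which phase they are in, and section 2.8 expects the bundle to alter how children are admitted locally.

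Randomising hospitals to crossover dates does not balance who is admitted after crossover. The mixed model in section 8.2 adjusts for hospital, rollout time and district, and none of these corrects a change in case mix caused by the bundle. If the admitted population changes, the primary estimate mixes transfers avoided with a change in who is counted. Because 3.8.1 governs data capture, records never collected cannot be recovered later by an analysis plan.

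**Working it through.** **1. Is there one population?** No. Sections 3.8.1, 3.8.3 and 5.1 give three bases, and 3.4 does not choose between them. No section says whether a child held in ED and then retrieved counts as admitted.

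**2. The plan's own figure.** Inputs from section 8.1: 14 hospitals, 4 steps (5 periods), 18 patients per hospital-period, 25% against 12.5%, ICC 0.1, two-sided 5%. The split 3/4/4/3 is from Figure 2. The Hussey-Hughes variance is

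v = I·s²(s² + T·τ²) / [(I·U − W)s² + (U² + I·T·U − T·W − I·V)τ²]

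- I = 14, T = 5, U = 35, W = 375, V = 103.
- With the control-rate variance 0.25 × 0.75 = 0.1875: τ² = 0.01875 and s² = 0.9 × 0.1875/18 = 0.009375.
- v = 0.013535/7.790625 = 0.001737, so the standard error is 0.0417.
- 0.125/0.0417 − 1.96 = 1.04, which gives power 0.851.
- The average-rate variance gives 0.914, and the mean of the two binomial variances gives 0.921.

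The stated power of over 85% is reproduced and is not in dispute. It rests on an admission-based rate.

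**3. What a change in admissions alone would do.** Take 100 control admissions with 25 transfers (the 25% of section 8.1). Keep transfers at 25 and let admissions change by a fraction g, so the measured proportion is 25/[100(1 + g)]. The values of g are assumptions, because the documents give none.

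| g | Measured proportion | Apparent change, points |
|---|---|---|
| −10% | 25/90 = 27.8% | +2.8 |
| +20% | 25/120 = 20.8% | −4.2 |
| +50% | 25/150 = 16.7% | −8.3 |
| +100% | 25/200 = 12.5% | −12.5 |

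At g = +20% the artefact is 4.2/12.5, or one third of the target effect. With the average-rate variance, the planned design would declare this artefact significant with probability about 0.18. At +50% the probability is about 0.57. It would take a doubling of admissions to mimic the whole target effect.

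**4. What making all presentations the primary base would cost.** Let a be the share of presentations admitted (an assumption), with all transfers among those admitted.

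- a = 0.8 gives 20% against 10%. Power at 1,260 children is 0.74-0.83, or 0.82-0.90 if all 1,575 presentations are counted.
- a = 0.5 gives 12.5% against 6.25%. Power is 0.50-0.61 at 1,260 children, or 0.78-0.88 if all 2,520 are counted.

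The ranges span the control-rate and average-rate variances.

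**The case against.** The strongest reply is that admission is plainly the working base: the synopsis, 3.8.1, the consent waiver in 5.2, the historical screen and the sample size all use it. On this view 3.8.3 only explains why there are no exclusions, and section 2.8 describes where a child is cared for, not a change in recorded admission status. No section says that the bundle lowers the admission threshold, and nasal high-flow is reserved for children in whom standard oxygen has failed, so extra mild admissions are conjecture. Much of this stands. The size of any shift is unsupported, and the wording conflict is narrow enough to settle by clarification. It does not dispose of the point, because 3.4 and 5.1 leave the base open and nothing in the design holds admission practice constant.

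A reader might go further and infer that control-phase children retrieved straight from ED drop out of the data, hiding a true benefit. For example, if 20% of 25 control transfers were lost, the control proportion would be 20/95 = 21.1% instead of 25%. The documents do not support this as a finding. Section 2.5 describes the 108 retrieved infants as a subset of the 216 admitted, section 8.1 quotes its 25% rate among admitted children, and 5.1 makes transfer itself a route into the data. Section 2.1 does describe children in South-East Queensland formerly staying in ED until retrieval, so the status of such children needs stating, but loss of their data is not shown.

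A reader might also infer that all presentations must become the primary denominator. That is a debatable trade-off. It dilutes the outcome (step 4 of the working), goes beyond the waiver for admitted patients in 5.2, and no longer matches the HBCIS-based historical data. Presentation could itself respond to the community engagement in the project.

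**Conclusion.** The point holds as a conflict between current sections with a conditional consequence. Three sections define the population differently and the primary outcome names no denominator. If 3.8.1 is followed literally, entry depends on a post-crossover decision by unblinded staff, and the transfer proportion could shift without any transfer being avoided.

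Neither size nor direction is established. The 4.2-point illustration assumes 20% more mild admissions, unchanged transfers and a 25% control rate. Fewer admissions would move the proportion the other way. The stated power is not affected.

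**What to change.** 1. Reconcile sections 3.8.1, 3.8.3, 5.1 and 3.4, and the synopsis, into one population: children aged 0-4 years meeting the clinical criteria who are admitted to a participating hospital or transferred from it, explicitly including transfers direct from ED. Apply the same screen in control and intervention phases, and name this population as the denominator in 3.4.
2. Pre-specify two sensitivity analyses that do not depend on the admission decision: transfers per eligible EDIS respiratory presentation aged 0-4 years, using aggregate counts, and transfers per hospital-month. The second moves with epidemic volume, so it needs the same adjustment for time as the primary model.
3. Report admissions per presentation by phase, so that a change in admission practice is visible.
4. Keep the 25% planning rate in section 8.1, with a note that its base is admitted children.

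The cost is modest: a little more analysis work on an EDIS export that is already planned, and a check that the waiver (5.2) and the Public Health Act approval (5.1 and 5.2) cover direct-from-ED transfers and aggregate presentation counts. The primary denominator need not become all presentations.
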